2.4. Study Design

2.4.1. Overall Design

Study I4V-MC-JAHO (JAHO) addendum is an open-label therapy in a subpopulation of Black patients with severe AA. Approximately 20 adult patients will be enrolled into Study JAHO addendum.

Patients must self-identify as Black or African American for race. Patients must have a current AA episode of more than 6 months' duration prior to screening (Visit 1), with at least 50% scalp involvement at screening AND Baseline (Visits 1 and 2) with no spontaneous improvement (no more than a 10-point reduction in SALT) over the past 6 months. Patients with a current episode of severe or very severe AA of more than 8 years will not be eligible for inclusion in the study unless episodes of regrowth, spontaneous or under treatment, have been observed on the affected areas of the scalp over the past 8 years. Photographs at screening must be submitted to Sponsor's designee for the confirmation of severe AA prior to enrollment.

All procedures to be conducted during the study, including the timing of all procedures, are indicated in the SOA (Section 2.2). Section 9.4.4 of the JAHO(e) protocol describes the collection of laboratory samples; [Appendix 2](#), [Appendix 4](#), and [Appendix 5](#) list the specific laboratory tests that will be performed for this study. Study governance considerations are described in detail in [Appendix 3](#).

2.4.1.1. Period 1: Screening (-35 to -5 days)

The duration of the Screening Period is between 5 and 35 days prior to Visit 2 (Week 0). Therapies that must be washed out or discontinued before initiation of therapy (Visit 2) are listed in exclusion criterion [10]. Patients who receive a PPD skin test at Visit 1 will return 48 to 72 hours later to read the skin test. Patients who are eligible for herpes zoster vaccine (per local guidelines) and have not previously received the vaccine will be encouraged to do so prior to initiation. Vaccination with the live herpes zoster vaccination (single injection) must occur at least 28 days (4 weeks) prior to enrollment. Vaccination with the nonlive herpes zoster vaccine requires 2 injections administered at least 8 weeks apart. It is recommended that patients who have initiated vaccination with the non-live herpes zoster vaccine receive the second dose at least 4 weeks prior to enrollment. For both vaccines, completion of the vaccination may require rescreening the patients to comply with the maximum allowed duration of the screening period. In addition, investigators should review the vaccination status of their patients and follow the local guidelines for vaccination of those ≥ 18 years of age with nonlive vaccines intended to prevent infectious disease prior to entering patients into the study.

At Screening (Visit 1), photographs of the scalp will be obtained from all patients. Views will include the right lateral, frontal, left lateral, forward tilt, and posterior. Up to 4 additional close-up views will be taken with and without cross-polarization lens of the left and right temporal area, the crown, and a representative patch selected by the physician, when applicable. Medical history and photographic data obtained at screening will be sent to the Sponsor's designee who will confirm the diagnosis of AA prior to initiation of therapy at Visit 2. Patients who meet all of the inclusion criteria (Section 2.5.1) and none of the exclusion criteria (Section 2.5.2) will continue to Visit 2.

2.4.1.2. Period 2: Open-Label Treatment (Weeks 0-52)

At Visit 2 (Week 0, Baseline), study eligibility for each patient will be reviewed on the basis of all inclusion (Section 2.5.1) and exclusion (Section 2.5.2) criteria and laboratory test results. Patients who meet all eligibility criteria will proceed to initiation of therapy and begin the 52 weeks open-label treatment (Study Period 2).

At Visit 2, after laboratory samples are collected and all assessments are completed, patients will take the first dose of IP in the clinic.

During Study Period 2, procedures and medications will be prohibited as listed in Section 2.6.7.2

At Baseline (Visit 2), photographs of the scalp and eyebrows/eyelashes will be obtained from all patients. Additional close-up views of the left and right temporal area, the crown, and the same representative patch selected at screening by the physician will be taken. Close-up photographs will be taken with and without a cross-polarization lens. After baseline, photographs of the scalp and close-up photographs will be repeated at Week 4, 8, 12, 24, 36, 44, 52 visits and in case of ET visit. Photographs of the eyebrows/eyelashes will be captured at these visits only from patients who have AA involvement (ClinRO ≥ 1) of those areas at Baseline, as assessed by investigator (see SOA [Section 2.2] and Section 2.8.1.4). Missed photographs after screening

will not be considered a protocol violation. Detailed requirements for photography are located in the Photography Manual.

The primary efficacy endpoint will be at Week 52 (Visit 11).

2.4.1.3. Period 3: Posttreatment Follow-Up

Patients who complete the study through Visit 11 (Week 52) will have a posttreatment follow-up visit (Visit 801) approximately 28 days after the last dose of IP. Patients who have completed Week 52 and who will continue on marketed product beyond Week 52 do not need to complete Period 3 (Visit 801).

Patients who have received at least 1 dose of IP and discontinue early from the study must have an ET and return for the posttreatment safety follow-up visit (Visit 801) approximately 28 days after the last dose of IP.

Patients who have discontinued IP product but remain in the study for more than 28 days without IP will have an ET if they choose to discontinue early. However, a separate follow-up visit (V801) is not required.

2.4.2. Number of Participants

Twenty patients were enrolled into the addendum.

2.4.3. End of Study Definition

End of study is the date of the last visit or last scheduled procedure shown in the SOA (Section [2.2](#)) for the last patient.

2.4.4. Scientific Rationale for Study Design

Baricitinib has been evaluated in the JAHO and JAIR studies and shown to be efficacious in the treatment of severe AA. Therefore, the subpopulation addendum does not require a comparator arm.

2.4.5. Justification for Dose

Based on the JAHO study primary outcomes, 4-mg baricitinib resulted in a greater proportion of patients achieving a $SALT \leq 20$ compared with 2-mg baricitinib. Therefore, 4-mg baricitinib dose was selected as the treatment for this addendum.

2.5. Study Population

Prospective approval of protocol deviations to recruitment and enrollment criteria (also known as protocol waiver or exemption) is not permitted.

Study investigator(s) will review patient history and screening test results at Visit 1 and Visit 2 to determine if the patient meets all inclusion criteria and none of the exclusion criteria to qualify for initiation in the study. All screening activities must be completed and reviewed before the patient is enrolled. Photographs taken at Screening must be submitted to the Sponsor or designee for the verification of SALT score ≥ 50 and hair loss due to AA. Subjects must not be enrolled until verification has been confirmed.

2.5.1. Inclusion Criteria

Patients are eligible to be included in the study only if they meet **all** of the following criteria at screening:

Informed Consent

- [1] Are at least 18 years and ≤ 60 years for males (≤ 70 years of age for females) at the time of informed consent.

Note: Use local requirements to provide consent if the age of adulthood is defined as >18 years. Different upper age limits have been included for male and female patients based on difference in the prevalence of concomitant androgenetic alopecia.

- [2] Self-identify as Black or African American race.
- [3] Are able to read, understand, and give documented (electronic or paper signature) informed consent.

Type of Patient and Disease Characteristics

- [4] Have severe or very severe AA, as determined by all of the following:
 - a. Current AA episode of more than 6 months' duration and hair loss encompassing $\geq 50\%$ of the scalp as measured by SALT at Visit 1 AND Visit 2.
 - b. No spontaneous improvement (that is, no more than 10-point spontaneous reduction in SALT) over the past 6 months.
 - c. Current episode of severe or very severe AA of less than 8 years.

Note: patients who have severe or very severe AA for ≥ 8 years may be enrolled if episodes of regrowth, spontaneous or under treatment, have been observed on the affected areas of the scalp over the past 8 years.
- [5] Agree not to use any AA treatments during the study, including, but not limited to
 - a. systemic therapies (for example, methotrexate, cyclosporine, corticosteroids, JAK inhibitors, apremilast, dimethyl fumarate derivatives, hydroxychloroquine, mycophenolate-mofetil, IFN γ , azathioprine) and biologics (for example, monoclonal antibodies)
 - b. intralesional corticosteroid injections
 - c. topical therapies, including irritants and immunotherapies (for example, diphenylcyclopropenone)
 - d. phototherapy, including lasers
 - e. platelet-rich plasma injection
 - f. HMG-CoA reductase inhibitors or "Statins" (for example, simvastatin, simvastatin + ezetimibe) for treatment of AA, and
 - g. Cryotherapy.

Note: Treatment with bimatoprost ophthalmic solution for eyelashes may be continued if the patient has been on a stable dose for 8 weeks prior to enrollment. Treatment with finasteride (or other 5 alpha reductase inhibitors) or oral or topical minoxidil may be continued if the patient has been on a stable dose for 12 months and is anticipated to continue on a stable dose up until Week 36.

[6] Are male or nonpregnant, nonbreastfeeding female patients

- a. Male patients will either remain abstinent (if this is their preferred and usual lifestyle) or agree to use 2 forms of birth control (1 must be highly effective, see below) while engaging in sexual intercourse with female partners of childbearing potential and agree to not father a child while enrolled in the study and for at least 4 weeks after the last dose of IP. Men who are in exclusively same-sex relationships (when it is their preferred and usual lifestyle) are not required to use contraception.
- b. Female patients of child-bearing potential who are abstinent (if this is complete abstinence, as their preferred and usual lifestyle) or in a same-sex relationship (as part of their preferred and usual lifestyle) must agree to either remain abstinent or stay in a same-sex relationship without sexual relationships with males. Periodic abstinence (for example, calendar, ovulation, symptothermal, postovulation methods), declaration of abstinence just for the duration of a trial, and vaginal withdrawal are not acceptable methods of contraception.

Otherwise, female patients of childbearing potential must agree to use 2 forms of birth control, when engaging in sexual intercourse with male partners while enrolled in the study and for at least 4 weeks after the last dose of IP.

The following birth control methods are considered acceptable (the patient should choose 2 to be used with their male partners, and 1 must be highly effective):

- Highly effective birth control methods: oral, injectable, or implanted hormonal contraceptives (combined estrogen/progesterone or progesterone only, associated with inhibition of ovulation); intrauterine device or intrauterine system (for example, progestin-releasing coil); or vasectomized male (with appropriate postvasectomy documentation of the absence of sperm in the ejaculate).
- Effective birth control methods: condom with a spermicidal foam, gel, film, cream, or suppository; occlusive cap (diaphragm or cervical/vault caps) with a spermicidal foam, gel, film, cream, or suppository; or oral hormonal contraceptives that do not inhibit ovulation.

Note: When local guidelines concerning highly effective or effective methods of birth control differ from the above, the local guidelines must be followed.

- c. Females of nonchildbearing potential are not required to use birth control. They are defined as:

- women ≥ 60 years of age or women who are congenitally sterile, or
- women ≥ 40 and < 60 years of age who have had a cessation of menses for ≥ 12 months and a follicle-stimulating hormone test confirming nonchildbearing potential (≥ 40 mIU/mL or ≥ 40 IU/L), or women who are surgically sterile (that is, have had a hysterectomy or bilateral oophorectomy or tubal ligation).

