2.3. Objectives and Endpoints

Objectives	Endpoints
Primary Objective	
To describe the effectiveness of 4-mg baricitinib in achieving scalp hair regrowth in patients with severe AA	Percent change from baseline in SALT score at Week 52
Key Secondary Objectives (Treatment Period 2)	
To describe the effectiveness of 4-mg baricitinib in achieving regrowth as assessed by physician assessed signs and symptoms of AA	
 • Proportion of patients achieving SALT ≤ 20 from baseline through Week 52 • Proportion of patients achieving a SALT₅₀, SALT₇₅, and SALT₉₀ from baseline through Week 52 • Percent change from baseline in SALT score at Week 52 • Mean change from baseline in SALT through Week 52 • Proportion of patients achieving ClinRO Measure for EB Hair Loss 0 or 1 with ≥ 2-point improvement from Baseline through Week 52 (among patients with ClinRO Measure for EB Hair Loss ≥ 2 at Baseline) • Proportion of patients achieving ClinRO Measure for EL Hair Loss 0 or 1 with ≥ 2-point improvement from Baseline through Week 52 (among patients with ClinRO Measure for EL Hair Loss ≥ 2 at Baseline)
To describe the effectiveness of 4-mg baricitinib during open-label treatment as assessed by PRO measures	
 • Proportion of patients with PRO for Scalp Hair Assessment score of 0 or 1 with ≥ 2-point improvement from Baseline through Week 52 among patients with a score ≥ 3 at Baseline • Proportion of patients with PRO for Eyebrow Hair Loss score of 0 or 1 with ≥ 2-point improvement from baseline through Week 52 among patients with a score of ≥ 2 at Baseline • Proportion of patients with PRO for Eyelash Hair Loss score of 0 or 1 with ≥ 2-point improvement from baseline through Week 52 among patients with a score of ≥ 2 at baseline • Proportion of patients with ≥ 1-point improvement in body hair areas (nose, beard, genital) as measured by the Body Hair Symptoms and Impact scale at Week 52 • Mean change in bothersome score on each area of hair loss (nose, beard, genital) as

Objectives	Endpoints
	
measured by the Body Hair Symptoms and Impact scale at Week 52
 
 Proportion of patients who rate their AA as much improved or very much improved on the Patient Global Impression of Change scale at Week 52

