- f. Platelet-rich plasma within 8 weeks prior to enrollment.
- g. Phototherapy (Ultra Violet therapy and laser on scalp lesions) within 4 weeks prior to enrollment.
- h. HMG-CoA reductase inhibitors or “statins” (for example, simvastatin, simvastatin + ezetimibe) for treatment of AA within 4 weeks prior to enrollment.
- i. Cryotherapy for treatment of AA within 4 weeks prior to enrollment.
- j. Finasteride (or other 5 alpha reductase inhibitors) or minoxidil (topical or oral) within 8 weeks prior to enrollment, unless the subject has been on a stable dose for at least 12 months AND is anticipated to continue on a stable dose up until Week 36
- k. Immunosuppressants (for example, methotrexate, cyclosporine, dimethyl fumarate derivatives, mycophenolate-mofetil, IFN γ , azathioprine) within 8 weeks of enrollment.
- l. Apremilast or hydroxychloroquine within 4 weeks prior to enrollment.

Medical Conditions in General

- [11] Are largely or wholly incapacitated, permitting little or no self-care, such as being bedridden.
- [12] Have uncontrolled arterial hypertension characterized by a repeated systolic blood pressure >160 mm Hg or diastolic blood pressure >100 mm Hg in a seated position.
- [13] Have had any major surgery within 8 weeks prior to screening or will require major surgery during the study that, in the opinion of the investigator (in consultation with Lilly or its designee), would pose an unacceptable risk to the patient if participating in the trial.
- [14] Are immunocompromised and, in the opinion of the investigator, at an unacceptable risk for participating in the study.
- [15] Have experienced any of the following within 12 weeks of screening: myocardial infarction, unstable ischemic heart disease, stroke, or New York Heart Association Stage III/IV heart failure.

- [16] Have a history of VTE, or are considered at high risk for VTE, as deemed by the investigator, or have 2 or more of the following risk factors for VTE:
- a) Aged >65 years
 - b) body mass index >35 kg/m²
 - c) Oral contraceptive use and current smoker status
- [17] Have a history or presence of cardiovascular, respiratory, hepatic, gastrointestinal, endocrine, hematological, neurological, or neuropsychiatric disorders or any other serious and/or unstable illness that, in the opinion of the investigator, could constitute an unacceptable risk when taking IP or interfere with the interpretation of data.

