2.6.7.1. Permitted Medications and Procedures

The following medications are permitted during the study:

- Topical corticosteroids except on the scalp, eyebrows, and eyelids.
- Topical calcineurin inhibitors except on the scalp, eyebrows and eyelids.
- Intranasal, ophthalmic, or inhaled steroid use.

- A maximum of 2 intra-articular or soft tissue (bursa, tendon, and/or ligament) corticosteroid injections are allowed.
- Nonlive vaccinations such as seasonal vaccination, nonlive herpes zoster (for subjects who become eligible during the trial), and/or all emergency vaccinations, such as rabies or tetanus vaccinations.
- Bimatoprost ophthalmic solution (if on stable dose for 8 weeks prior to enrollment).
- Finasteride (or other 5 alpha reductase inhibitors) or oral or topical minoxidil, if on a stable dose for 12 months prior to enrollment.
- HMG-CoA reductase inhibitors or “statins” (for example, simvastatin, simvastatin + ezetimibe) for treatment of hypercholesterolemia and the prevention of cardiovascular disease.

Nutraceuticals (for example, Viviscal, Nutrafol) and other over-the-counter hair products may be used if patients are currently using them at baseline. They should be encouraged to continue with the same amount and frequency during the study. Oil on the scalp should be avoided at scheduled visits to reduce potential glare for photographs.

Treatment with concomitant therapies for other medical conditions, such as diabetes and hypertension, is permitted during the study.

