2.9. Statistical Considerations

2.9.1. Sample Size Determination

Study JAHO addendum initially intended to screen approximately 80 patients to enroll 60 patients, as a sample size considered sufficient for subject improvement in hair growth. Subsequent enrollment resulted in a sample size of 20 patients. The sample size of approximately 20 patients is sufficient to provide descriptive information on subject improvement in hair regrowth. As the addendum objectives were designed as descriptive in nature, it did not rely on power calculations and therefore, a sample size of approximately 20 patients is sufficient for further description of treatment outcomes with this population.

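### Stable use of 5-alpha-reductase inhibitors and minoxidil is anticipated only to Week 36, and no analysis rule covers a change before the Week 52 primary visit

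*Protocol*

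**What the plan says.** Three places in the Protocol govern these agents.

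- **Section 2.5.1, note to inclusion criterion [5].** A patient who has been stable for 12 months may continue a 5-alpha-reductase inhibitor or minoxidil if he or she "is anticipated to continue on a stable dose up until Week 36".
- **Section 2.5.2, exclusion criterion [10]j.** Recent use excludes a patient unless the dose has been stable for at least 12 months "AND is anticipated to continue on a stable dose up until Week 36".
- **Section 2.6.7.1.** The permitted list reads "Finasteride (or other 5 alpha reductase inhibitors) or oral or topical minoxidil, if on a stable dose for 12 months prior to enrollment". It looks back from enrollment and states nothing about stability afterwards.

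The primary endpoint in Section 2.3 is "Percent change from baseline in SALT score at Week 52", and Section 2.4.1.2 places it at Visit 11. On design, Section 2.4.4 states that "the subpopulation addendum does not require a comparator arm", and Section 2.4.2 that "Twenty patients were enrolled into the addendum". Section 2.9.3.1.2 specifies observed-case analysis without imputation. Section 2.9.4.1 reports the mean percent change with its standard error and 95% confidence interval.

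**The concern.** The stability horizon in the two eligibility criteria matches the main study's Week 36 endpoint, not the addendum's Week 52 endpoint. Section 1 explains that the endpoint was moved later because response was slower and the hair regrowth cycle longer in this population. Weeks 36 to 52 are therefore the period that the extension was meant to capture, and they are the weeks that the wording leaves uncovered.

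These agents are used for hair growth, and the outcome is scalp hair. In a randomized comparison, background changes would tend to occur in both arms. With one arm and 20 patients, any effect of stopping or changing such an agent is mixed into the Week 52 summary and cannot be separated from the effect of baricitinib. The plan neither identifies these patients nor shows the result without the affected values.

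**Working it through.** The plan has no figure to reproduce here. Section 2.9.1 says of the addendum that "it did not rely on power calculations". The check sets the sections side by side and then gives an illustrative size.

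**Step 1: the uncovered window.** Stability is anticipated to Week 36 (Sections 2.5.1 and 2.5.2) and the endpoint is at Week 52 (Section 2.3). The gap is 52 − 36 = 16 weeks, and 16/52 = 30.8% of the treatment period. It ends at the primary visit.

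**Step 2: does another provision close it?**

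- Section 2.6.7.1 encourages nutraceutical users to keep amount and frequency constant during the study. It has no matching sentence for 5-alpha-reductase inhibitors or minoxidil, so a stated on-study condition is lacking from Week 0, not only after Week 36.
- Section 2.6.7.2 prohibits AA therapies but exempts those listed in Section 2.6.7.1.
- Section 2.7.2 ends participation for an AA agent that the protocol does not allow. A dose change in a permitted agent does not clearly meet that.
- Section 2.9.4.1 offers an optional further analysis that cuts data only at permanent treatment discontinuation.
- The SAP contains no analysis of this addendum's Week 52 endpoint. Its censoring rules (SAP Section 4.4) address study-drug discontinuation, remote visits, retreatment and treatment switch. Its example of a deviation (SAP Section 4.16) is excluded concomitant therapy, which a permitted agent is not.

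**Step 3: illustrative shift in the primary mean.** If k patients each have their percent change moved by D points in the same direction, the mean of n patients moves by k × D / n. Here n = 20 (Section 2.4.2). The documents give neither k nor D, so both are assumptions. The table gives absolute shifts, which could be in either direction.

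| k | D = 10 | D = 20 | D = 30 | D = 50 |
|---|---|---|---|---|
| 1 | 0.5 | 1.0 | 1.5 | 2.5 |
| 2 | 1.0 | 2.0 | 3.0 | 5.0 |
| 3 | 1.5 | 3.0 | 4.5 | 7.5 |
| 4 | 2.0 | 4.0 | 6.0 | 10.0 |

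For example, 4 × 50 / 20 = 10.0. Observed-case analysis can reduce n. If only 12 patients were observed (also an assumption), four affected patients would move the mean by 4 × 10 / 12 = 3.3 to 4 × 50 / 12 = 16.7 points.

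**Step 4: scale.** The half-width of the 95% confidence interval is t(0.975, n − 1) × SD / √n. For n = 20 it is 14.0, 18.7 or 23.4 points at an assumed SD of 30, 40 or 50. One affected patient is small against this, while four at the upper end are not negligible. The interval describes sampling error and makes no allowance for such a shift.

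**Step 5: the SALT ≤20 rate.** One patient crossing the threshold moves it by 1/20 = 5 percentage points. That is true of any cause at this sample size.

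**The case against.** The strongest reply is that the Week 36 wording is a forecast made once, at entry, and not a licence to change dose at Week 37. A reader might infer that the protocol expressly permits changes after Week 36. It does not: the eligibility note speaks of continuing a stable treatment, and no section states such a permission. What stands is the silence. Section 2.6.7.1 sets no on-study condition, and no analysis rule follows from a change.

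Exposure is also narrow. A new start would fail the 12-month condition in Section 2.6.7.1 and, if given for AA, would fall under the prohibition in Section 2.6.7.2. Section 2.6.7 requires patients to consult the site before taking any new medication. The concern is thus largely limited to patients already using these agents at entry, and there may be none.

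Enrollment is complete, so rewording the eligibility criteria cannot affect the 20 patients. This is correct, and it leaves Section 2.6.7.1 and the analysis as the parts that still matter.

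Finally, the objectives are descriptive, and Section 2.9.3.1.4 already summarizes concomitant medication. Use would be visible, but frequencies and percentages need not reveal a dose change or link it to a patient's Week 52 SALT value.

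**Conclusion.** The concern holds in a limited form. The mismatch between Week 36 and Week 52 is plain in the current text, and nothing in either document defines how a change in these agents before the primary visit is handled. Whether it affects the result is unknown, because the documents give no count of users and no record of changes. With D assumed to be 10 to 50 points, the mean of 20 moves by 0.5 to 2.5 points for one patient and by 2 to 10 for four.

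A reader might go further and conclude that the Week 52 result is biased in favor of baricitinib. The documents do not support that. A raised dose could add regrowth and a reduced or stopped one could cause loss, so the direction is open. No source in the documents supports any particular effect size. This is a cheap improvement to an uncontrolled summary of 20 patients, not a defect that invalidates it.

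**What to change.** 1. **Text.** The sponsor should reconcile the note to inclusion [5], exclusion [10]j and Section 2.6.7.1 with each other and with the Week 52 endpoint. Section 2.6.7.1 is the one that can still affect enrolled patients. Which clinical rule should apply is the sponsor's decision, and none is proposed here.
2. **Listing.** Before database lock, prespecify a listing of patients who use a 5-alpha-reductase inhibitor or minoxidil, with any start, stop or dose change after baseline. If there were no changes, one sentence in the report settles the matter.
3. **Sensitivity summary.** Prespecify one repeat of the Week 52 percent change in SALT and of SALT ≤20 that excludes SALT values recorded after such a change.
4. **Primary analysis.** Leave the observed-case primary analysis as it is. If post-change values were set to missing there as well, the primary and the sensitivity summary would give the same Week 52 figure for any change before that visit, and the comparison would be lost.

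The cost is one listing and one extra table with a smaller n. One item needs checking first. Section 2.6.7 requires concomitant medication to be recorded on the eCRF but does not say that dose or dose changes are captured. If they are not, the affected patients would have to be queried.
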